2 OBJECTIVES AND OUTCOME MEASURES

	Objective	Endpoints
Primary:	Evaluate severe acute respiratory syndrome coronavirus 2 (SARS-CoV-2) transmission following exposure in Kindergarten through 12th grade schools.	
 Proportion and number of students with positive COVID-19 test following known exposure. Proportion and number of staff with positive COVID-19 tests following known exposure. Proportion and number of exposures undergoing the test-to-stay protocol that result in additional transmission. Time to test positivity among those exposed to SARS-CoV-2 and undergoing the test-to-stay protocol.
Secondary #1:	Characterize the effect of individual-level mitigation measures (e.g., masking) on SARS-CoV-2 spread.	
 Proportion and number of masked students with positive COVID-19 test who were exposed to SARS-CoV-2 from masked versus unmasked individuals. Proportion and number of masked staff with positive COVID-19 test who were exposed to SARS-CoV-2 from masked compared to unmasked individuals Proportion and number of unmasked students with positive COVID-19 tests who were exposed to SARS-CoV-2 from masked compared to unmasked individuals Proportion and number of unmasked staff with positive COVID-19 tests who were exposed to SARS-CoV-2 from masked compared to unmasked individuals
Secondary #2	Characterize the effect of exposure setting on SARS-CoV-2 spread.	
 Proportion and number of students with positive COVID-19 test after indoor vs. outdoor exposure. Proportion and number of students with positive COVID-19 test after athletic vs. classroom exposure. Proportion and number of students with positive COVID-19 test after bus vs. classroom exposure.
Secondary #3:	Describe COVID-19-related school absences for up to	
 Total number of school days missed due to symptoms after exposure.

	14 days following SARS-CoV-2 exposure.	
• Total number of school days missed due to isolation after positive COVID-19 test.• Total number of school days missed due to quarantine after SARS-CoV-2 exposure.
--	--	---

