5.3 Enrollment/Baseline

Participants or their parent/legal guardian will provide informed consent (or assent). Applicable informed consent from the participant or parent/legal guardian (and assent if applicable) for all participants will be documented. After consent, the participant will be assigned a unique ID by the school nurse or administrator. The school nurse or administrator will collect study-related variables via a spreadsheet using one of two different methods. The school nurse may use AirTable, a system designed by Technology and Data Solutions, or standard excel spreadsheets, which will be sent to the research team. The research team will have access to individual-level data but will not have access to names or other identifiers. While the study team will have access to the consents completed via REDCap, the team will not know which unique ID belongs to which individual.

The following information will be collected from the student at the time of enrollment. Information may be collected directly from the participant, their parent/legal guardian, or via a school nurse. The information will include the following:

- Participant demographics (age, sex, English proficiency, and vaccination status)
- Mitigation data collection including whether the participant was masked or unmasked, and vaccination status (if known)
- Exposure details include when exposure occurred, where it occurred, and if the individual who caused the exposure was masked or unmasked

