8.1.2 Secondary Endpoints

Secondary Objective #1: Characterize the effect of individual-level masking on SARS-CoV-2 spread.

Secondary #1 Endpoints:

- Proportion and number of masked students with positive COVID-19 test who were exposed to SARS-CoV-2 from masked versus unmasked individuals.
- Proportion and number of masked staff with positive COVID-19 test who were exposed to SARS-CoV-2 from masked compared to unmasked individuals
- Proportion and number of unmasked students with positive COVID-19 tests who were exposed to SARS-CoV-2 from masked compared to unmasked individuals
- Proportion and number of unmasked staff with positive COVID-19 tests who were exposed to SARS-CoV-2 from masked compared to unmasked individuals

Secondary Objective #2: Characterize the effect of exposure setting on SARS-CoV-2 spread.

Secondary #2 Endpoints:

- Proportion and number of students with positive COVID-19 test after indoor vs. outdoor exposure.
- Proportion and number of students with positive COVID-19 test after athletic vs. classroom exposure.
- Proportion and number of students with positive COVID-19 test after bus vs. classroom exposure.

Secondary Objective #3: Describe COVID-19-related school absences for up to 14 days following within-school SARS-CoV-2 exposure.

Secondary #3 Endpoints:

- Total number of school days missed due to symptoms after exposure.
- Total number of school days missed due to isolation after positive COVID-19 test.
- Total number of school days missed due to quarantine after SARS-CoV-2 exposure.

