1.5 Primary Analysis

- Objective: The proportion of students/staff with positive COVID-19 test following known within-school exposure and the proportion of exposures undergoing the test-to-stay protocol that result in additional transmission will be summarized overall, by student or staff, by school district, by school level.
 - To account for the within-school correlation of outcomes, 95% CI will be estimated for the proportion using a generalized estimating equations approach using a working independence correlation structure (Zeger et al. 1988).
 - Objective: Days to test positivity among those exposed to SARS-CoV-2 and undergoing the test-to-stay protocol will be summarized by median and interquartile ranges and nonparametric estimate of test positivity probability will be plotted.

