1.6 Secondary Analysis

- Objective: The proportion of students/staff who reported masking and unmasking will be summarized and presented in a bar chart to see the trend by testing day.
 - The primary analysis will be repeated for masked and unmasked participants (students and staff) separately.
 - The primary analysis will be repeated for masked and unmasked source of exposure separately.
- Objective: School absences will be analyzed by absences due to symptoms, positive COVID-19 test, or due to quarantine for exposure to SARS-CoV-2.
 - To account for the within-school correlation of outcomes, analyses will be conducted using a generalized estimating equations approach using a loglink suitable for count outcomes, with a working independence correlation structure (Zeger et al. 1988).

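### Vaccination status is recorded, where known, as mitigation data, but no prespecified Manuscript 1 analysis stratifies or adjusts by it, so the mask results may be confounded in either direction

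*SAP*

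**What the plan says.** **Data collected.** Protocol 5.3 lists vaccination status twice at enrollment. It appears once among the demographics and once beside masking: "Mitigation data collection including whether the participant was masked or unmasked, and vaccination status (if known".

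**Aim.** Protocol section 2 states Secondary Objective 1 as "Characterize the effect of individual-level mitigation measures (e.g., masking) on SARS-CoV-2 spread", and SAP 1.1 repeats that aim for Manuscript 1. Masking is given there as an example. Protocol 8.1.2 is narrower: "Characterize the effect of individual-level masking on SARS-CoV-2 spread".

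**Analysis.** SAP 1.6 plans two repeats of the primary analysis: "The primary analysis will be repeated for masked and unmasked participants (students and staff) separately" and "The primary analysis will be repeated for masked and unmasked source of exposure separately". The analysis being repeated is in SAP 1.5. Its proportions "will be summarized overall, by student or staff, by school district, by school level", and the model serves to give an interval: "95% CI will be estimated for the proportion using a generalized estimating equations approach using a working independence correlation structure". No covariate is named in either section.

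**Vaccination elsewhere.** SAP 1.7 allows exploratory subgroup analyses without naming any. Protocol 8.2 plans summary statistics from enrollment data. The SAP names vaccination as an analysis item only in 3.6 (Manuscript 3), where it is described alongside demographics.

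**The concern.** The protocol itself classes vaccination with masking as an individual mitigation measure. The objective asks for the effect of such measures, yet the planned output is a set of proportions by mask status with vaccination left out.

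If masked and unmasked participants differ in how many are vaccinated, and vaccination changes the chance of a positive test, then a difference between the mask groups is partly a vaccination difference. A reader of Manuscript 1 would have no prespecified result from which to judge whether this had happened. The introductions to both documents say the results are meant to inform school policy on mitigation, so a mask contrast reported under an effect objective is likely to be read causally.

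**Working it through.** The documents state no event count, uptake, vaccine effect or mask effect for this comparison, and Protocol 8.3 says there was no sample size calculation. There is no planned figure to reproduce. The check is one of text, followed by an illustration.

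**Step 1: is vaccination used anywhere in Manuscript 1?** SAP 1.1 to 1.7 name it in no endpoint, stratum, model or subgroup. The breakdowns carried over from 1.5 are student or staff, district and school level. The GEE supplies a clustered interval for a proportion and does not adjust for covariates. So the mask-stratified proportions are unadjusted for vaccination.

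**Step 2: how large could the distortion be?** Let VE be the proportional reduction in the risk of a positive test from vaccination (vaccine risk ratio = 1 − VE). Let pM and pU be the vaccinated shares among masked and unmasked participants. Assume no true mask effect, the same VE in both mask groups, and no other confounder. Then

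crude RR = (1 − VE × pM) / (1 − VE × pU).

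All values of VE, pM and pU below are assumptions.

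| Vaccinated, masked vs unmasked | VE 30% | VE 50% | VE 80% |
|---|---|---|---|
| Equal shares | 1.00 | 1.00 | 1.00 |
| 15% vs 5% | 0.955/0.985 = 0.97 | 0.925/0.975 = 0.95 | 0.88/0.96 = 0.92 |
| 50% vs 30% | 0.85/0.91 = 0.93 | 0.75/0.85 = 0.88 | 0.60/0.76 = 0.79 |
| 60% vs 30% | 0.82/0.91 = 0.90 | 0.70/0.85 = 0.82 | 0.52/0.76 = 0.68 |
| 60% vs 20% | 0.82/0.94 = 0.87 | 0.70/0.90 = 0.78 | 0.52/0.84 = 0.62 |
| 30% vs 50% | 0.91/0.85 = 1.07 | 0.85/0.75 = 1.13 | 0.76/0.60 = 1.27 |

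If VE is zero, every row gives 1.00.

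**Step 3: the same on the difference scale.** With r0 the risk in the unvaccinated, the spurious risk difference is −VE × (pM − pU) × r0. At VE 50% this is −0.5 × 0.30 × r0 = −0.15 r0 for 60% vs 30%, and −0.5 × (−0.20) × r0 = +0.10 r0 for 30% vs 50%. The documents give no r0, so the ratio scale is used for illustration.

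**Step 4: which contrast does this describe?** It describes masked versus unmasked participants, the first repeat in SAP 1.6. The endpoints in Protocol 8.1.2 hold the participant's mask status fixed and compare masked with unmasked sources. The participant's vaccination distorts that second contrast only if it is associated with the source's masking. The documents do not say whether it is.

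**The case against.** **Confounding is not shown.** The documents give no uptake, no association between masking and vaccination, and no vaccine effect. This stands. A reader might infer that the mask results are confounded by vaccination and that they flatter masks. The documents support only that they may be confounded, and the direction is open.

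**Entry does not depend on vaccination.** The background (Protocol 1.1.1) describes quarantine rules that refer to vaccination, and Protocol 3.2 ties enrollment to avoiding quarantine. A reader might infer that vaccination governs entry. The criteria in Protocol 4.1 and SAP 1.2 contain no vaccination condition. If enrollment did lean towards unvaccinated contacts, vaccination would vary less and the distortion would shrink. A cross-tabulation would settle this.

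**Status is not known for everyone.** Protocol 5.3 qualifies the item, so it cannot be read as complete for all participants. This also stands, and it limits any adjustment.

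**Masking is partly school policy.** Breakdowns by district and school level capture some of that, but they do not separate vaccinated from unvaccinated participants within a school.

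**There are other routes for vaccination.** SAP 1.7 is permissive and names nothing. An overall enrollment summary does not show vaccination by mask status and adjusts nothing. Neither closes the gap.

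**The plan is descriptive.** No listed endpoint concerns vaccination, and SAP 1.6 commits to separate proportions, without a ratio, difference or test. That is a fair reading of the methods, but it conflicts with an aim worded as an effect. If description is all that is intended, the SAP should say so.

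**Conclusion.** The point holds in limited form. Vaccination status is collected, where known, as mitigation data, and no prespecified Manuscript 1 analysis stratifies or adjusts by it. The mask-stratified proportions cannot carry the effect language of the objective.

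The possible distortion in the participant-mask contrast runs from none to substantial. With no true mask effect, the crude risk ratio lies between 0.62 and 1.27 over the assumed values tabulated. It is 1.00 with equal vaccinated shares, 0.82 at 60% vs 30% and 1.13 at 30% vs 50%, each at a vaccine risk ratio of 0.5. These figures rest wholly on assumed uptake and vaccine effect and do not estimate the bias in this study. They also do not carry over to the source-mask contrast. The overall student and staff proportions in the primary analysis are not affected.

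**What to change.** In SAP 1.6:

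1. Tabulate vaccination (yes, no, unknown) by participant mask status, and report the primary proportion by vaccination status. State that the unknown group is shown, because the SAP's General Statistics Principles drop unknowns from percentage denominators in summary tables unless otherwise specified. That rule concerns tables and does not settle how a regression should treat unknowns.
2. Beside the crude proportions, report a masked versus unmasked risk difference, once for participant masking and once for source masking, from the school-clustered GEE. Adjust for vaccination status (with unknown as its own level), student or staff, school level, exposure setting and the other party's mask status. Protocol 5.3 collects where the exposure occurred and both mask statuses. Repeat the analysis in participants with known vaccination status as a check. Protocol 8.2.2 already foresees an identity-link GEE for a risk difference between schools, so the method is not new to the study.
3. Describe the crude mask-stratified proportions as descriptive, not as effects.

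The cost is SAP wording and a little more analysis, with no new data. Intervals will be wider if events are few, and the documents give no event or school counts from which to judge whether the full covariate set is feasible. Confounding will remain among participants of unknown vaccination status, which is why the restricted check is needed.

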1.7 Subgroup Analysis

Exploratory subgroup analysis may occur from the information collected as part of this study.

Manuscript #2 Test-to-Stay in K-12 Schools after SARS-CoV-2 Exposure: a mitigation strategy for optionally-masked schools?

Date	June 17, 2022
Corresponding author	[name]
Lead statistician	[name]
Statistical advisor	[name]
Project leader	[name]
Target journal	TBD

History of changes

Date	Version	Summary of changes
May 16, 2022	1.0	Manuscript submitted
June 14, 2022	1.0	Revision submitted
June 17, 2022	1.0	SAP was documented

2.1 Specific Aims

- To evaluated the impact of a test-to-stay (TTS) program on within-school transmission and missed school days in optionally masked kindergarten through 12th grade schools during a period of high community severe acute respiratory syndrome coronavirus 2 (SARS-CoV-2) transmission.

2.2 Data

TTS data collected from K-12 students and staff with a non-household, within or outside of school exposure to SARS-CoV-2 between November 29, 2021 and January 28, 2022 under school districts in North Carolina (NC) employing optionally masking.

2.3 Study Population

- **Enrolled population:** participants with at least one test with valid results.
- **Analysis eligible population:** participants who were tested positive or had a negative follow-up test at day 5 or later, and completed follow-up among those enrolled

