2.5 Handling of Missing Data

No imputation will be performed; Missing data will be excluded from all denominators.

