3.2 Data

TTS data collected from K-12 students and staff with household exposures within 4 districts and 1 charter school in North Carolina (NC) employing universal masking.

- Establish population cutoff
 - [name] (Statistical programmer): Here are the number of household exposures with test results on or after days 5, 7, and 9: \geq Day 5 = 282; \geq Day 7 = 251; \geq Day 9 = 214
 - [name] (Project leader): Given that ~65% of population made it into analysis eligible population for day 9, we will use this day as the cutoff, which is consistent with CDC guidance for household close contacts

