3.3 Study Population

- **Enrolled population:** participants enrolled after household exposures after treating re-exposures within the FU testing period as one long exposures from the first exposure, n=322

Re-exposures after the FU testing period (treat as unique cases)	Re-exposures within the FU testing period (treat as one long exposures) → pick the re-exposed record by A_SL.REEXSEQ in (.2) because two participants got positives after the re-exposure
---	---

Re-exposure records	Confirmed positive	Days to positive, median (min, max)	Note	Re-exposure records	Confirmed positive	Time to positive, median (min, max)	Note
10	5	4 (2, 8)	10 re-exposure records are from 10 participants, which means their initial exposure was not a household close contact.	26	2	8 & 9	26 records are from 13 participants

- **Analysis eligible population:** participants who were tested positive or had a negative follow-up test at day 9 or later, and completed follow-up, n=265

Total records	Exposure period	# enrolled after treating re-exposures (Total records - 13)	# analysis eligible
335	1/8/22 – 2/15/22	322	265

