3.7 Sensitivity Analysis

- Objective: Repeat the main analyses among study participants who had a positive test on or after the day of exposure.
- Objective: Broaden primary analysis for considered positives that include presumed positives, defined as those who developed symptoms but did not receive a subsequent negative test.
- Objective: Estimate range of household SAR by using positivity reported in published literature. For individuals who were tested on day 9 or later, we will use existing TTS data. For participants who did not receive a test on day 9 or later, we will impute values to obtain a range, with the following visual representation as a plot:
 - SAR for the analysis eligible pop
 - SAR for the analysis eligible pop + presumed positives
 - SAR for the analysis eligible pop + presumed positives + 25% of the people with missing data as positive
 - SAR for the analysis eligible pop + presumed positives + 40% of the people with missing data as positive
 - SAR for the analysis eligible pop + presumed positives + 55% of the people with missing data as positive

→ Rationale, reports of SAR in household close contacts range from 25-55% positive. We would like to use published literature to give a range based on our existing data.

→ To account for the within-school correlation of outcomes, the 95% confidence interval (CI) for the proportion was estimated using an over dispersed binomial regression model. For sparse data, confidence intervals for SAR estimates were computed using the Clopper-Pearson approach.

→ The study team decided not to include to the manuscript.

References

Zeger SL, Liang K-Y, Albert PS. Models for Longitudinal Data: A Generalized Estimating Equation Approach. *Biometrics*. 1988;44(4):1049-1060.

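### In Manuscripts 2 and 3 the analysis-eligible set takes positives from any day but never-positives only with a late negative, so the attack-rate denominator depends on the outcome

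*SAP*

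**What the plan says.** SAP 2.3 (Manuscript 2) enrols anyone with at least one valid result and limits the analysis-eligible set to "participants who were tested positive or had a negative follow-up test at day 5 or later, and completed follow-up among those enrolled". SAP 3.3 (Manuscript 3, household exposures) uses "participants who were tested positive or had a negative follow-up test at day 9 or later, and completed follow-up, n=265", out of 322 enrolled. Neither definition puts a day limit on the positive test.

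SAP 2.6 and 3.6 report SAR and TAR in both populations. SAR, or test positivity, is a secondary endpoint in both manuscripts (SAP 2.4, 3.4). In Manuscript 2 the TAR is a primary endpoint, measured among close contacts who themselves enrolled. On missing data, SAP 2.5 states "No imputation will be performed; Missing data will be excluded from all denominators", and SAP 3.5 has the same sentence.

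SAP 3.7 describes a range analysis: "For participants who did not receive a test on day 9 or later, we will impute values to obtain a range". Its lowest imputed value is "SAR for the analysis eligible pop + presumed positives + 25% of the people with missing data as positive", followed by 40% and 55%. The section ends "The study team decided not to include to the manuscript", which I read as referring to this range. SAP 2.8 and 3.7 also plan to count as positive those with symptoms and no later negative test.

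The day-9 cutoff was chosen in SAP 3.2 from counts introduced by "Here are the number of household exposures with test results on or after days 5, 7, and 9": 282, 251 and 214. The stated reason begins "Given that ~65% of population made it into analysis eligible population for day 9".

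**The concern.** Take two Manuscript 3 participants whose last test was on day 3. The one who tested positive is in the denominator; the one who tested negative is out. Entry is decided partly by the result that the SAR is meant to measure. If people stop testing for reasons unrelated to infection, this removes non-cases selectively and the eligible SAR is too high.

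The enrolled SAR errs the other way. It keeps people with only early negatives and counts them as not positive through the end of follow-up, although they were observed only to their last test. If the missing-data rule instead treats them as missing, they leave that denominator too, and the two figures become the same.

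If people who stopped were infected more often than those who stayed, the eligible SAR may be too low. The protocol's definition of completion (3.3) lists symptoms among the accepted reasons for incomplete testing, so this cannot be ruled out.

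At stake is the positivity reported in both manuscripts and, in Manuscript 2, the primary TAR, because its denominator consists of enrolled participants to whom the same eligibility rule applies. Manuscript 3's TAR has close contacts as its denominator, so this rule does not act on it directly.

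**Working it through.** **1. The plan's own counts (SAP 3.3).** 335 records − 13 = 322 enrolled, as stated. Eligible: 265. Outside: 322 − 265 = 57, and 57/322 = 17.7%. Eligible share: 265/322 = 82.3%.

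**2. The 65% figure (SAP 3.2).** 214/322 = 66.5% and 214/335 = 63.9%. The figure is the share with a day-9-or-later test, not the eligible share.

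**3. Ratio of the two SARs.** Let P be the number of positives, all in both populations. Eligible SAR = P/265 and enrolled SAR = P/322, so the ratio is 322/265 = 1.215 whatever P is. If the missing-data rule removes all 57 from the enrolled denominator, the ratio is 1.000.

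**4. What is known about P.** The SAP does not give it. An eligible person without a day-9-or-later test must be a positive, so P is at least 265 − 214 = 51 if 214 counts participants. If 214 counts records before merging, and all 13 merged participants gain a late test, P is at least 265 − 227 = 38. These are floors.

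**5. Bias of the eligible SAR.** Let q be the share of the 57 who were or became positive. Relative bias = (P/265) / ((P + 57q)/322) − 1, which is zero at q = P/265. P = 71 and P = 80 are illustrative assumptions.

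| P | q = 0 | q = 10% | q = 25% | break-even q |
|---|---|---|---|---|
| 38 (floor) | +21.5% | +5.7% | −11.6% | 14.3% |
| 51 (floor) | +21.5% | +9.3% | −5.0% | 19.2% |
| 71 | +21.5% | +12.5% | +1.2% | 26.8% |
| 80 | +21.5% | +13.4% | +3.1% | 30.2% |

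Only the ceiling is free of P. At q = 25% the sign changes with P.

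**6. Direction when stopping is unrelated to infection.** A simulation assumed tests on days 1, 3, 5, 7 and 9; 15/30/30/15/10% of the infected turning positive at those tests; and a 93% or 95% chance of continuing after each test. With true risk 30% and 21.1% or 15.5% excluded, the eligible SAR was 33.6% or 32.5%, the enrolled SAR 26.5% or 27.5%, and Kaplan-Meier with censoring at the last negative 30.0%. So the two proportions lie either side of the truth, and the censored estimate recovers it.

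**7. How far the fix might move Manuscript 3.** Illustration only. It assumes P = 51, counts on the 322 basis, none of the 57 with a late test, and independent censoring. Last test before day 5: 322 − 282 = 40; day 5–6: 282 − 251 = 31; day 7–8: 251 − 214 = 37; total 108 = 51 + 57. Splitting the 51 positives in proportion gives 18.9, 14.6 and 17.5. Kaplan-Meier = 1 − (1 − 18.9/322)(1 − 14.6/282)(1 − 17.5/251) = 17.0%, against 19.2% eligible and 15.8% enrolled.

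**8. Manuscript 2.** No counts are given, so nothing can be computed.

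**The case against.** A positive participant must isolate, so a late test cannot be required of positives. An evaluable set shown beside the full enrolled set is a familiar convention, and the plan does report both. That stands as a reason for having the set. It does not make either proportion an estimate of the attack rate.

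The consequence may be modest. SAR is secondary in both manuscripts. The shift in step 7 is about 2.3 points before rounding, inside the exact 95% interval of 14.7–24.5% for 51/265 (before clustering). That also stands, though the error is systematic and does not shrink with more data.

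Stronger readings are tempting, but the documents do not support them:

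- A reader might infer that the omitted range was the only analysis covering people without a late test. It was not. The enrolled SAR includes them, unless the missing-data rule removes them, and the presumed-positive analyses reach some. It was the only one that varied their unknown outcome.
- A reader might infer that the eligible SAR is biased downward at the SAP's own 25%. That result depends on floor counts and reverses at 71 or 80 positives.
- A reader might apply 25–55% to the 57 as a likely rate. SAP 3.7 takes it from overall positivity in household contacts; for people already negative on early tests it is probably high.
- A reader might assume that all 57 stopped with early negatives. Eligibility also requires completed follow-up, and the SAP does not say how that applies, so some may be positives or have late negatives.
- A reader might hold that enrolled and eligible figures must coincide under the missing-data rule. In Manuscript 2 that is strained, since one valid result is enough to enrol. In Manuscript 3 it is open, because SAP 3.7 itself speaks of missing data for those lacking a day-9 test.

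**Conclusion.** The point holds and should be fixed. In both manuscripts the eligible denominator depends on the outcome. In Manuscript 3 this affects 57 of 322 enrolled, and the eligible SAR is 1.215 times the enrolled SAR, provided every positive is in both populations and the 57 stay in the enrolled denominator. The same ratio caps the upward bias, reached only if none of the 57 was or became positive. Actual size and sign are unknown because the number of positives is not given.

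If stopping is unrelated to infection, the eligible and enrolled proportions are an upper and a lower bound. If people who stopped were infected more often than the eligible SAR, the upper bound fails. Manuscript 2, including its primary TAR, has the same structure but cannot be sized.

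**What to change.** - In both manuscripts, estimate the SAR (and Manuscript 2's TAR) among all enrolled as the cumulative probability of a positive test by a fixed, stated day, censoring never-positives at their last negative test. Use the Turnbull estimator for interval-censored data, or Kaplan-Meier, with a confidence interval that allows for clustering. SAP 1.5 already plans a nonparametric positivity curve for Manuscript 1.
- Do not use delayed-entry risk sets for participants notified late. A positive at a late first test is left- or interval-censored, which Turnbull handles; delayed entry would set those positives against too few people.
- Keep the enrolled and eligible proportions, labelled as bounds under independent censoring.
- In Manuscript 3, report the 25/40/55% range as a stress test, say that it is overall household positivity and probably high for people with early negatives, and reconcile it with the no-imputation rule in SAP 3.5. The documents give no comparable range for the non-household exposures of Manuscript 2, so it should not be carried over.
- State whether people with only early negatives count as missing, and what completed follow-up means, including for positives. Correct the 65% in SAP 3.2: it is the share with a day-9-or-later test, and the eligible share is 82.3%.

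Cost: SAP wording and a re-run on data already held. Manuscript 2's results would need revising; SAP Manuscript 2's change history shows submission and revision before its SAP was documented. The SAR is no longer a simple count over a count, and it assumes independent censoring, which symptom-driven stopping may strain. The presumed-positive analyses are a check on that in both manuscripts, and the range is a further check in Manuscript 3.
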